## 8 CORRELATIVE STUDIES

### 8.1 Specific Aims

- Assess the phenotypic and functional changes of post-HCT DEC-C/venetoclax therapy on B and T cell subsets.
- Correlate changes in B and T cell subsets with clinical data, including DEC-C/venetoclax dosing schedules and patient characteristics.

### 8.2 Study methods:

We will assess the effect of DEC-C/venetoclax on immune subsets in post-HCT AML. Using B- and T-cell mass cytometry (CyTOF) panels in stimulated/unstimulated peripheral blood mononuclear cell (PBMC) samples, we will perform immunophenotyping prior to treatment, following pre-remission therapy, during post-remission therapy, and at the end of treatment (EOT). Specimens that will be collected are described in [Table 1](#). Correlative data interpreted in the context of clinical data and study outcomes.

#### 8.2.1 Assess the phenotypic and functional changes of post-HCT DEC-C/venetoclax therapy on B and T cell subsets

Immunophenotyping will be performed to identify quantitative and functional changes in B-cell and T-cell subsets with the intent of furthering our understanding of the mechanism(s) of immune-related adverse events. These assays will include flow cytometry/CyTOF and cytokine analysis.

We will interrogate T and B cell signaling, and immune function/composition, by flow cytometry or single cell mass cytometry (CyTOF) using cryopreserved PBMCs isolated from patients pre-treatment and at serial timepoints post-treatment. The Cytec Aurora, will allow up to 20 spectra at one time without compensation issues. Using a 15-20 antibody immune

oncology panels and standard operating procedures for the staining of clinical and preclinical samples to define the immune phenotype. Specific lymphocyte subsets can also be characterized with intracellular cytokines as well as cell surface markers of activation or polarization. For more highly multiplexed analyses a Helios mass cytometer (CyTOF) will be employed to measure up to 35-40 protein parameters on a per cell basis. We will utilize validated anti-human T-cell and B-cell antibodies for a comprehensive immune cell analysis.

Sample	Timepoint			
	Pre-Tx	On Treatment		EOT
		Intense C1D22	Intense C2D22	
Blood- PBMC isolation	X	X	X	X
Blood- serum/plasma isolation	X	X	X	X

**Figure 4. Time points for clinical correlates**

Modulation of cytokines will also be monitored by Luminex leveraging serum or plasma isolated from whole blood from patients pre-DEC-C/venetoclax treatment and at serial timepoints post-treatment. The Luminex system (Millipore/Thermo-Fisher) will be used with Millipore plates and beads on biospecimens collected from patients. Standard manufacturer-recommended protocols will be used, and MAGPIX/xPONENT will be used for readout of cytokine levels. Standard curves generated from positive controls will be used to quantitate the concentration of the cytokines.

Immunological data generated from these assays will be integrated and correlated with patient outcomes (infection vs. no infection and response vs. no response).

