**Notes:**

[figure not shown]
1. Informed consent must be obtained before any screening assessments are performed. Screening assessments are to be performed within 14 days prior to Day 1 of Cycle 1 unless otherwise noted. Assessments performed as standard of care within the screening window may be used for screening. Baseline characteristics include but are not limited to demographics, medical and surgical history, extent of disease, prior anti-cancer treatment.
2. Vital Signs to include: Blood pressure (BP), heart rate (HR) and temperature. To be done at least once on days indicated and thereafter, ideally prior to any receipt of study drug. Any additional recordings per local site's standard of care/ treating physician discretion.
3. Review and capture of all concomitant medications will be performed as indicated. Concomitant medications include prescription medications and over-the-counter preparations used by a patient within at least 14 days prior to first dose of protocol-defined treatment and continuing through at least the 28-day Follow-Up study visit. After signing informed consent, adverse events will be collected and followed at least until 28 days after a patient's final protocol-directed treatment with DEC-C/venetoclax (whichever occurs last) or until initiation of another anti-cancer therapy – whichever occurs first.
4. Surveillance for toxicity related to DEC-C/venetoclax to establish RP2D. For patients enrolled in the dose exploration (or dose de-escalation) part of the study, dedicated surveillance including satisfactory assessment of the physical exam and safety labs is required to help detect evidence of past or present DLT as having occurred during the first 28 days of protocol-indicated treatment. Expedited reporting of Dose Limiting Toxicity (DLT) required as outlined in [Section 5.2.4](#). See [Section 5.2.4](#) for definition of DLT and toxicities which, if experienced during the first 28 days after initiating protocol-indicated treatment, shall be considered dose limiting.
5. Hematology includes white blood cell count with differential, hemoglobin, hematocrit, and platelet count. Blood Chemistry to include sodium, potassium, chloride, bicarbonate or carbon dioxide, blood urea nitrogen (BUN), creatinine, glucose, total bilirubin, AST, ALT, alkaline phosphatase, calcium, albumin, and total protein.

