6. One standard 12-lead electrocardiogram (ECG) using local site equipment during screening and EOT visits. Additional ECGs as clinically indicated.
7. For women of childbearing potential: Serum pregnancy test required during screening and either serum or urine pregnancy test required  $\leq 3$  days prior to first dose of protocol-indicated treatment and at End-of-Treatment. A woman of childbearing potential is defined as any female who has experienced menarche who has not undergone surgical sterilization (e.g. bilateral tubal ligation, total hysterectomy, or bilateral oophorectomy) at least 4 weeks prior to first dose of protocol-indicated treatment, or who is not postmenopausal. Menopause is defined clinically as 12 months of amenorrhea in a woman over 45 in the absence of other biological or physiological causes.
8. Patients must have at least 2-3 mL of bone marrow aspirate material obtained within 14 days of beginning treatment on this study. Post-enrollment tissue to be collected on Cycle 1 Day 22, Cycle 2 Day 22 (only if C1 Day 22 marrow is

involved), post-remission Cycle 3 Day 1 (acceptable windows up to 3 days before or after); and at End-of-Treatment ( $\leq 14$  days after treatment was discontinued) or at time of suspected progressive disease.

[figure not shown]
9. On a day of a bone marrow biopsy, matching peripheral blood pharmacodynamic (PD) blood samples are to be drawn PRIOR to procedure for correlative research. At any time during the study, if additional biopsy is performed as standard-of-care, then a sample of the tissue, if available, may be requested for research purposes. Pharmacodynamic studies will be drawn to assess the impact of DEC-C/venetoclax on immune function/recovery during treatment and correlated with clinical/study outcomes.
10. All patients will have next generation sequencing (NGS) performed on their relapsed marrow and all subsequent marrows performed while on study. If the standard of care NGS report is available prior to enrollment, this should not be repeated. If NGS testing is not indicated per the institutional standard of care, additional bone marrow aspirate may be sent to VUMC and NGS will be performed as a research test.

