### **8.2.2 Correlate changes in B and T cell subsets with clinical data, including DEC-C/venetoclax dosing schedules and patient characteristics.**

As DEC-C/venetoclax combination therapy is evaluated in the corresponding phase II trial, the study data will be analyzed in combination with the immune subset data from SA1. Combining these datasets will provide important clinical context in an immunocompromised population. Clinical features, including time from HCT to relapse, dosing of DEC-C/venetoclax, immunosuppression, infectious complications, and non-relapse mortality events will be correlated with immune subset data. Body surface area (BSA) and body mass index (BMI) after HCT will be correlated with the depth and duration of cytopenias, including absolute lymphocyte count. This approach will extend SA1, identify clinical populations at-risk for toxicity, and inform study design and dosing in future DEC-C/venetoclax studies.

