### 9.3.1 General Analysis Considerations

Continuous variables (e.g., age) will be summarized using the minimum, 25th, 50th (median), 75th, and maximum values along with the mean and standard deviation, as appropriate. Generally, rank based nonparametric tests will be used to compare continuous variables among patient subgroups. Categorical variables (e.g., objective response) will be summarized in frequency tables and compared among patient subgroups using the chi-square test. Linear regression and logistic (or ordinal logistic) regression will be used to construct multivariable models for continuous, binary, and ordinal variables, as appropriate. In addition to ORR, the distributions of progression-free and overall survival will be estimated using the Kaplan-Meier method. We will consider statistical comparisons statistically, but not necessarily clinically, significant for  $p<0.05$ .

Dose limiting toxicity (see [Section 5.2.4](#)) will be monitored in this phase II clinical trial using a Bayesian approach. A maximum of 34 patients will be enrolled and toxicity monitoring will begin when the 6th patient is evaluable for toxicity. It is expected that the toxicity rate is maintained at approximately 20% (maximum probability of DLT of 0.2, prior distribution (1,1), cohort size 1, and posterior probability  $> 80\%$ ). Pursuant to this rule, patients will be monitored according to the stopping boundaries outlined in [Table 10](#). For example, the protocol will pause for review due to excessive toxicity if 2 or more DLTs are experienced by the first 6 patients treated. 9 DLTs will be allowed among 34 patients treated.

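### The correlative infection comparison has no common time window, so an immune marker linked only to remission can appear linked to infection

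*Combined protocol and SAP*

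**What the plan says.** Section 8.2.1, in the text after Figure 4, states the comparison: "Immunological data generated from these assays will be integrated and correlated with patient outcomes (infection vs. no infection and response vs. no response"). Section 8.2.2 adds that "infectious complications, and non-relapse mortality events will be correlated with immune subset data". Neither section gives a start or end date for counting infections, a grade, a rule for patients who die or stop early, or a statistical method.

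Section 9.3.1 gives the general methods. Continuous variables are compared between subgroups by rank tests and categorical ones by chi-square. For models, "Linear regression and logistic (or ordinal logistic) regression will be used to construct multivariable models for continuous, binary, and ordinal variables, as appropriate". Kaplan-Meier is named only for progression-free and overall survival.

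Infections reach the database as adverse events. Note 3 to the schedule tables says "adverse events will be collected and followed at least until 28 days after a patient's final protocol-directed treatment with DEC-C/venetoclax", "or until initiation of another anti-cancer therapy" if that comes sooner. Section 7.1.5 restates the 28-day limit, counted from end of treatment. Section 7.10 then schedules survival contact only.

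Treatment duration depends on the marrow result. Section 7.4 schedules a second pre-remission cycle only when the C1D22 marrow is involved. Section 5.2.6.3 opens the post-remission phase to patients who clear marrow blasts, and Note 12 allows up to 12 months of it.

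The sample table in Section 8.2.1 lists blood before treatment, at C1D22, at C2D22 and at end of treatment (EOT). Note 8 limits the third: "Cycle 2 Day 22 (only if C1 Day 22 marrow is" involved).

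**The concern.** Whether a patient is ever recorded with an infection depends on how long infections are recorded as well as on how often they occur. Here the length of recording is tied to marrow clearance. If remitters are observed several times longer than the others, more of them will have an infection on file even when the monthly risk is the same in everyone. Any marker that differs by remission then differs by infection status too. Section 8.2.1 tests the same markers against response, so a marker that differs by remission is a realistic case.

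Two related problems follow from the sampling schedule. An infection may precede the C1D22 sample, so unless the pairing is specified a marker could be measured after the event it is meant to explain. And C2D22 and EOT blood are not comparable by response: the first exists only in patients with an involved C1D22 marrow, and the second is drawn at a time that depends on response.

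At stake is the use Section 8.2.2 foresees: identifying patients at risk of toxicity and informing design and dosing of later studies.

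**Working it through.** The plan states no figure for infection follow-up, so there is none to reproduce. The steps below build the observation windows from protocol durations and then test the comparison under stated assumptions.

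**1. Windows.** Cycles last 28 days, the adverse event tail is 28 days, post-remission therapy lasts at most 12 months, and a month is 30.44 days.
- No remission, one cycle: 28 + 28 = 56 days = 1.8 months.
- No remission, two cycles: 56 + 28 = 84 days = 2.8 months.
- Remission after one cycle, full post-remission therapy: 12 + 1.8 = 13.8 months.
- Remission after two cycles, full post-remission therapy: 12 + 2.8 = 14.8 months.

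The lower figure is a range because Section 7.4 ties the second cycle to an involved marrow, while Note 15 describes it for patients with at least a partial response. Death or new therapy shortens any window. Relapse or toxicity shortens the long ones, and delays for count recovery lengthen them.

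**2. Effect of the window alone.** With hazard λ per month, equal in all patients, P(infection) = 1 − exp(−λt):

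| λ (assumed) | t = 2.8 months | t = 13.8 months |
|---|---|---|
| 0.05 | 13% | 50% |
| 0.10 | 24% | 75% |
| 0.20 | 42% | 94% |

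**3. False-positive rate.** Simulation with N = 34 (Section 9.3.1) and 35% remitters (the design's alternative response rate, used as an assumed remission fraction). The marker is normal, shifted by d SD in remitters, with no effect on infection hazard. Non-remitters are observed for 2.8 months and remitters for 1.8 months plus their post-remission time. Tests are two-sided at 0.05 (sidedness assumed), with 1,500 runs per setting. At a rate of 20% the simulation error is √(0.2 × 0.8 / 1,500), about 1 percentage point.

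| Setting | λ = 0.05 | λ = 0.10 | λ = 0.20 |
|---|---|---|---|
| Ever/never, rank test, d = 1, full 12 months | 14.9% | 20.3% | 23.4% |
| Ever/never, d = 1, median 6 months post-remission | 8.7% | 11.9% | 12.8% |
| Ever/never, d = 0, full 12 months | 4.7% | 5.0% | 4.7% |
| Time to first infection, censored (Cox score test), d = 1, full 12 months | 5.4% | 5.0% | 6.3% |

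A repeat at hazards of 5 to 15% per month with d = 1 gives about 16 to 23% with full follow-up and 8 to 11% with the 6-month median.

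**4. Where the effect fades.** With 15% remitters, d = 1 and full follow-up, the ever/never rate is 9 to 11%. With an early hazard of 0.2, 0.4 or 0.8 per month up to 2.8 months and 0.05 afterwards (35% remitters, d = 1), it is 8.5%, 5.5% and 4.5%.

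**5. Sample timing.** EOT blood falls near the end of treatment: about 28 to 56 days (0.9 to 1.8 months) without remission, and up to 12.9 to 13.8 months with full post-remission therapy. Only the pre-treatment and C1D22 samples are scheduled for every patient.

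**The case against.** The plan does not say how infection will be scored. A reader might infer that early deaths and non-responders are counted as infection-free. No section says so: they would count that way only if no infection was recorded before capture ended, and an early or fatal infection counts as an infection. The plan does not exclude a common window, Section 9.3.1 is not stated to govern Section 8, and its methods are offered in general terms. This stands as a limit on the wording of the point. It does not remove the gap, because no other method is named for this comparison.

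A reader might also take 65 to 85% of patients (the complement of the 35% and 15% response rates) to be on the short path. That equates the primary response with entry to the post-remission phase. Entry needs marrow blast clearance, so patients with a morphologic leukemia-free state, a secondary outcome, can also enter. The off-treatment list in Section 5.2.13 does not name non-response as a reason to stop, so the short window is itself inferred from the schedule. The long window is a maximum.

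Note 3 sets a minimum for capture, and Section 9.3.2 counts drug-related events as treatment-emergent through the end of the study. Some later infections may therefore be recorded, but not systematically.

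Finally, the size rests on hazards and marker shifts that the documents do not supply. If infections are commoner in active leukaemia, the bias could shrink or reverse. That objection also stands.

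**Conclusion.** The point holds as a gap in definition with a real but conditional consequence. A yes/no infection outcome with no common window, analysed by methods that ignore time at risk, can turn a marker–remission association into an apparent marker–infection association.

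The 16 to 23% rate is an upper case: maximum follow-up in every remitter, a 1 SD marker difference by remission, 35% remitters and an equal constant hazard. A 6-month median gives 8 to 11%. With no marker–remission link the comparison keeps its nominal 5%. The direction in the actual trial cannot be settled from the documents.

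The correlative aims are outside the primary and secondary objectives, no trial decision depends on them, and the primary endpoint is unaffected. This is a cheap improvement.

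**What to change.** In Section 8.2.1:
- Replace the yes/no infection outcome with time to first infection, at a grade stated in advance. Censor at the end of adverse event capture, treat death without infection as a competing event, and relate markers to infection by the cause-specific hazard.
- Use pre-treatment markers with time counted from C1D1. Use C1D22 markers only for infections after that sample, as a landmark analysis in patients still under capture.
- For response versus no response, use the pre-treatment level and the change to C1D22. Report C2D22 and EOT blood descriptively.

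A common day-84 window is a tempting alternative, but one-cycle patients may leave capture near day 56. A 56-day window would hold the error rate (3.5 to 4.9% with d = 1 and full follow-up) but drops later infections that bear on the dosing aim in Section 8.2.2. Censored time to first infection keeps them.

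The cost is analysis wording and a little more analysis work, since the event dates and samples are already planned. Events will be few. With 12 remitters (35% of 34) at 13.8 months and 22 others at 2.8 months, a hazard of 0.05 gives 12 × 0.50 + 22 × 0.13, about 9 first infections, and 0.10 gives 12 × 0.75 + 22 × 0.24, about 14. Models should stay small. The change removes the artefact of unequal observation. It does not remove a true difference in infection risk between patients in and out of remission.

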### **8.2.2 Correlate changes in B and T cell subsets with clinical data, including DEC-C/venetoclax dosing schedules and patient characteristics.**

As DEC-C/venetoclax combination therapy is evaluated in the corresponding phase II trial, the study data will be analyzed in combination with the immune subset data from SA1. Combining these datasets will provide important clinical context in an immunocompromised population. Clinical features, including time from HCT to relapse, dosing of DEC-C/venetoclax, immunosuppression, infectious complications, and non-relapse mortality events will be correlated with immune subset data. Body surface area (BSA) and body mass index (BMI) after HCT will be correlated with the depth and duration of cytopenias, including absolute lymphocyte count. This approach will extend SA1, identify clinical populations at-risk for toxicity, and inform study design and dosing in future DEC-C/venetoclax studies.

## **9 PLANNED STATISTICAL METHODS:**

### **9.1 General Considerations**

Statistical support for this study will be provided by the Department of Biostatistics at Vanderbilt University Medical Center with analyses being performed by or under the direction of a faculty member in biostatistics.

### **9.2 Disease Assessments**

For the purposes of this analysis, responses will be assessed in accordance with the International Working Group (IWG) response criteria in acute myeloid leukemia.

### **9.3 Dose De-escalation Design**

Assuming a historical ORR of 15%, per the phase II efficacy trial, Simon's optimal two-stage design calls for a total of 34 patients. A preliminary efficacy assessment will be performed following enrollment of the first 20 patients. If  $\geq 3/20$  enrolled patients achieve a CR, this is sufficient to continue enrollment for the remainder of the study.

If  $>9/34$  patients respond, we will reject ( $p<0.05$ ) the null hypothesis that the true response rate of the regimen is less than or equal to 15%. If the true response rate is 35% or greater, this study design has 80% probability of rejecting the null hypothesis. If the true response rate is low at 15%, the probability of early termination is 60% with an expected sample size of 19 patients.

The maximum number of patients enrolled ( $n=51$ ) reflects an anticipated drop out of 15% ( $n=5$ ) and enrollment of 6-12 additional patients if dose level 0 is deemed toxic.

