**Statistical Analysis:**

Assuming a historical ORR of 15%, per the phase II efficacy trial, Simon's optimal two-stage design calls for a total of 34 patients. A preliminary efficacy assessment will be performed following enrollment of the first 20 patients. If  $\geq 3/20$  enrolled patients achieve a CR, this is sufficient to continue enrollment for the remainder of the study. If  $\geq 9/34$  patients respond, we will reject ( $p < 0.05$ ) the null hypothesis that the true response rate of the regimen is less than or equal to 15%. If the true response rate is 35% or greater, this study design has 80% probability of rejecting the null hypothesis. If the true response rate is low at 15%, the probability of early termination is 60% with an expected sample size of 19 patients.

Toxicity will be monitored in the expansion phase using a Bayesian approach. Toxicity monitoring will begin when the 6th patient is evaluable for toxicity. It is expected that the toxicity rate is maintained at approximately 20% (maximum probability of DLT of 0.2, prior distribution (1,1), cohort size 1, and posterior probability  $> 80\%$ ). Enrollment will be paused if toxicity exceeds this rate.

The maximum number of patients enrolled (n=51) reflects an anticipated drop out of 15% (n=5) and enrollment of 6-12 additional patients if dose level 0 is deemed toxic.

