## 1 INTRODUCTION

### 1.1 Background

Acute myeloid leukemia, excluding acute promyelocytic leukemia, is generally associated with poor clinical outcomes. Patients with poor-risk clinical and molecular features experience a shortened survival with a minority surviving beyond 5 years. Similarly, patients with high-grade myeloid malignancies, including myelodysplastic syndrome (MDS) and chronic myelomonocytic leukemia (CMML), are at risk for leukemic transformation with rates approaching 40%. For poor-risk patients, allogeneic HCT is the only potentially curative therapy, however, post-HCT relapse is common and as many 85% of poor-risk AML patients will experience recurrence of their underlying disease. In a registry analysis, 15% of post-HCT relapsed AML patients achieved a subsequent complete remission (CR). Less than 5% of patients who relapsed within 6 months, and 12% of patients who relapsed 6-24 months after HCT were alive at 3 years.

Dysregulation of anti-apoptotic proteins, including BCL2, is responsible for tumor maintenance and survival. Venetoclax is a selective BCL2 inhibitor that increases cell death/apoptosis in hematologic malignancies. In chronic lymphoid leukemia, a disease heavily reliant on the loss of apoptosis, overall response rates (ORR) exceed 80% with venetoclax. In AML, anti-apoptotic pathways are more heterogeneous. Venetoclax, in combination with DNMTis or low dose cytarabine, results in CR/CRi rates of 60-75% in the treatment naïve (TN) setting. Off-label use in the relapsed/refractory (R/R) disease is an emerging treatment paradigm with an ORR of 12-51%. In a series of post-HCT AML patients treated with venetoclax-based salvage therapies at Vanderbilt University Medical Center (16/21 with a DNMTi partner), our group reported that the combination is safe and effective with an ORR of 42.1%. Interrupting therapy in patients with a treatment response improved safety and reduced toxicity after HCT.

Based on our published experience, and other retrospective data in the R/R AML, this phase 2 trial will prospectively assess the ORR of venetoclax/DNMTi salvage therapy after allogeneic HCT. Partnering venetoclax with DEC-C combines the efficacy of venetoclax/DNMTi therapy with the convenience of an all-oral treatment regimen which will reduce the burden of treatment relative to conventional salvage therapies.

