## **2 STUDY OBJECTIVES**

### **2.1 Primary Objectives:**

1. To assess the effect of DEC-C/venetoclax on the investigator-assessed composite CR rate (CR/CRh/CRi)

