### 4.3 Exclusion Criteria:

1. Prior relapse or progression while receiving venetoclax or other commercially available or investigational BCL-2 inhibitor.
2. Anticancer therapy, including investigational agents  $\leq$  2 weeks or  $\leq$  5 half-lives of the drug, whichever is shorter, prior to C1D1. (Use of hydroxyurea is permitted).
3. Inadequate recovery from toxicity attributed to prior anti-cancer therapy to  $\leq$  Grade 1 (NCI CTCAE v5.0), excluding alopecia or fatigue.
4. History of allogeneic hematopoietic cell transplantation (HCT), or other cellular therapy product, within 3 months of signing consent.
5. Clinically active acute or chronic GVHD. Patients must be off calcineurin inhibitors for at least 4 weeks to be eligible.
6. Radiation therapy or major surgery within 3 weeks of signing consent.
7. Active, uncontrolled infection. Patients with infection under active treatment and controlled with antibiotics are eligible. Prophylaxis is acceptable.
8. Inability to tolerate oral medication, presence of poorly controlled gastrointestinal disease, or dysfunction that could affect study drug absorption.
9. Active documented central nervous system leukemia
10. Concurrent treatment with a non-permitted concomitant medication.
11. Other malignancy IF currently being treated or likely to be treated in next 6 months except for basal or squamous cell carcinoma of the skin or cervical carcinoma in situ.
12. Pregnancy or breastfeeding females
13. Known chronic alcohol or drug abuse
14. Clinically significant cardiovascular disease with major event or cardiac intervention within the past 6 months (e.g. percutaneous intervention, coronary artery bypass graft, documented cardiac heart failure) as determined by the investigator
15. Any other condition deemed by the investigator to make the patient a poor candidate for clinical trial and/or treatment with investigational agents.

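### The 15% null appears to be a complete-remission rate, while the endpoint tested against it is the broader CR/CRh/CRi

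*Combined protocol and SAP*

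**What the plan says.** Section 9.3 and the synopsis (Statistical Analysis) open with the same premise: "Assuming a historical ORR of 15%, per the phase II efficacy trial, Simon's optimal two-stage design calls for a total of 34 patients". Neither gives a reference. The hypothesis to be rejected is "the null hypothesis that the true response rate of the regimen is less than or equal to 15" per cent. The design target is stated as "If the true response rate is 35% or greater, this study design has 80% probability of rejecting the null hypothesis".

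The primary objective in Section 2.1 is "To assess the effect of DEC-C/venetoclax on the investigator-assessed composite CR rate (CR/CRh/CRi"). The only 15% response figure elsewhere in the documents is in Section 1.1, repeated in the synopsis background: "In a registry analysis, 15% of post-HCT relapsed AML patients achieved a subsequent complete remission (CR").

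The interim look is described as "A preliminary efficacy assessment will be performed following enrollment of the first 20 patients". Enrolment continues if at least 3 of 20 achieve a CR. The final cut-off is more than 9 of 34 in Section 9.3 and at least 9 of 34 in the synopsis. Section 9.3 thus uses three terms: ORR for the null, CR for the interim rule, and respond for the final rule.

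**The concern.** The trial has no control arm, so any statement that the regimen improves on past results rests on the 15%. For that statement to hold, the 15% must measure the same outcome as the primary endpoint. The documents suggest that it does not. Section 1.1 keeps its terms apart: it reports CR for the registry, CR/CRi for treatment-naïve venetoclax combinations (60-75%), and ORR for relapsed or refractory disease (12-51%). On the protocol's own usage, the registry 15% reads as CR alone.

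Adding CRh and CRi can only raise a response rate or leave it unchanged. If the 15% leaves them out, the matching composite null is at least 15% and may be higher. The trial could then pass because its definition of response is wider, with no gain over existing salvage. At stake is what a positive result would mean, not whether the binomial test is valid against 15%.

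**Working it through.** **Inputs from the documents.** Null 15%, alternative 35%, significance 0.05, power 80%, total 34, first look at 20 with continuation if at least 3 respond (Section 9.3); final cut-off more than 9/34 (Section 9.3) or at least 9/34 (synopsis).

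**Assumed input.** The historical CR/CRh/CRi rate is not in the documents. The values 18%, 20% and 25% are a range for illustration.

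**Step 1: the plan's own figures.** A search for the Simon optimal design for 15% against 35%, one-sided 0.05 and 80% power, gives: stop if at most 1/9 respond, declare success if at least 9/34. Its type I error is 4.7%, power 81.1%, early termination at 15% is 59.95%, and expected size is 9 + 25 × (1 − 0.5995) = 19.0. The stated 34, 80%, 60% and 19 all reproduce. The 15% is therefore the null that the sample size was built on.

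The looks as written (20, then 34) are a different rule. At 15% they stop early with probability 40.5%, and the expected size is 20 + 14 × (1 − 0.405) = 28.3. That mismatch, and the conflict between the two final cut-offs, are separate matters. All three rules are carried below to show that the conclusion does not depend on them.

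**Step 2: probability of passing at a true composite rate p.** For the written looks, with c the smallest passing count (10 for more than 9/34, 9 for at least 9/34):

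P(pass | p) = Σ over x = 3 to 20 of Bin(x; 20, p) × P(Bin(14, p) ≥ c − x)

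| True composite rate | Written looks, >9/34 | Written looks, ≥9/34 | Simon optimal (9, then 34), ≥9/34 |
|---|---|---|---|
| 15% | 2.4% | 5.8% | 4.7% |
| 18% | 7.1% | 14.3% | 11.8% |
| 20% | 12.5% | 22.5% | 18.8% |
| 25% | 33.5% | 48.4% | 41.4% |
| 35% | 80.4% | 88.9% | 81.1% |

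A gap of 3 points between the CR rate and the matching composite rate puts the chance of passing with no improvement above 5% under every rule. The ≥9/34 column with the written looks already starts at 5.8%, so its excess over 5% is not all due to the null. At 20% the rise from the 15% row is 10.1 points (>9/34) and 16.7 points (≥9/34).

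**Step 3: what a CR-alone comparison would require.** With all 34 patients, the exact (Clopper-Pearson) 95% interval is 12.9% to 44.4% for 9/34 and 15.1% to 47.5% for 10/34. Excluding 15% therefore needs 10 CRs. As a check, P(at least 10 of 34 | 15%) = 2.4%, below 2.5%, while P(at least 9 of 34 | 15%) = 5.9%. If the true CR-alone rate were 25%, 10 or more CRs would be seen about 34% of the time (33.5% with the written looks applied to CR, 33.6% for 34 patients without an interim look).

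**The case against.** The strongest reply is that no passage says the 15% comes from the registry. The text attributes it to a phase II efficacy trial. Even if it does come from the registry, the documents do not say whether that analysis counted remissions with incomplete recovery as CR. Both points stand: the link is an inference from the only matching number, and the CR-alone reading rests on the label in Section 1.1. They do not supply a justification, though. If the 15% has another source, that source is uncited and its response definition unstated.

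A second reply is that at a true rate of 18% to 25% the stated null is false, so rejecting it is not a type I error, and that passing needs an observed 26.5% (9/34) or 29.4% (10/34). This is correct. The test does what it says against 15%. The issue is the reading of a rejection as a gain over history.

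A reader might also infer that eligibility makes the matching null higher still, because the registry includes relapses within 6 months while the trial excludes "History of allogeneic hematopoietic cell transplantation (HCT), or other cellular therapy product, within 3 months of signing consent". The documents do not establish this. The early and late relapse figures in Section 1.1 are 3-year survival, not response. The exclusion runs from transplant to consent, not to relapse, so relapses at 3 to 6 months remain eligible, and an earlier relapse can enrol once 3 months have passed. The criteria also admit ECOG 2 and creatinine clearance down to 30 ml/min. How the registry patients were selected is not described. The population difference is a caveat whose direction and size are unknown.

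**Conclusion.** The point holds as an endpoint mismatch, by inference. An unreferenced 15%, matched in the documents only by a registry CR rate, is the null for a CR/CRh/CRi endpoint. If the 15% excludes CRh and CRi, a positive primary test supports the statement that the composite rate exceeds 15%, and not that it exceeds the historical rate. The chance of passing with no improvement is 7.1% to 33.5% (>9/34) or 14.3% to 48.4% (≥9/34) for a matching historical composite rate of 18% to 25%. Those rates are assumptions, so the size is conditional on them.

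Two stronger conclusions are not supported: that the 15% is known to be too low, and that patient selection adds a calculable amount to it.

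**What to change.** In Section 9.3 and the synopsis (Statistical Analysis):

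1. State the source of the 15%, the response definition behind it, and the population it describes.
2. Keep composite CR as the primary endpoint. Add a pre-specified CR-alone rate with an exact 95% confidence interval set against 15%, described as matched on endpoint and not on population.
3. State the probability of passing the final cut-off at true composite rates of 18%, 20% and 25%.
4. Unless the 15% is shown to be a composite rate, word the primary conclusion as *composite CR exceeds 15%*, and rest any statement about the historical CR rate on the CR-alone comparison.

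The cost is wording and one added analysis. CR, CRh and CRi are the components of the primary endpoint, so no patients, visits or procedures are added. The downside is lower power for the claim against history. CR alone cannot be more frequent than the composite, and 10 CRs in 34 are needed for the interval to exclude 15%.
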